8.1 Study Medication and Materials

8.1.1 Dosage Form, Manufacturing, Packaging, and Labeling

In this protocol, the term study medication refers to all or any of the drugs defined below.

- Lubiprostone 24 µg capsules.
- Placebo capsules to match Lubiprostone 24 µg.

Investigational material is encapsulated in clear orange soft gelatin capsules and packaged into 60 count high-density polyethylene (HDPE) bottles, including a rayon filler, induction sealed and closed with a child-resistant cap. Each bottle contains enough capsules to treat subjects for 28 days + a 2-day window during the Double-Blind Treatment Period, and will be labeled with a single-panel label including pertinent study information. As this study is double-blind, all study medication will be packaged, labeled, and dispensed in a blinded manner.

The bottle will contain a unique medication identification (MED ID) number and will be dispensed via the InteractiveVoice/ Web Response System (IVRS/IWRS), with 1 bottle dispensed per subject.

An IVRS/IWRS program will be used to manage inventory, assist the site in dispensing the proper investigational drug to the subjects, record accountability and support the return to sponsor or designee of these investigational drugs after study completion.

8.1.1.1 Investigational drug

Lubiprostone 24 µg and placebo will be supplied by the sponsor. All drugs supplied by the sponsor will be manufactured, tested, and released according to Good Manufacturing Practice (GMP).

8.1.1.2 Rescue Medication

A total of 10 mg of bisacodyl suppository (or an equivalent drug) may be prescribed as a standard rescue medication if a subject has no adequate BM for 3 consecutive days during the study. When bisacodyl suppository does not improve constipation, glycerin enema (or equivalent drug) may be given. Subjects are instructed to complete their diaries before using these drugs. No rescue medication may be used within 24 hours before and 48 hours after the start of the Double-Blind Treatment Period (Day1).

8.1.2 Storage

Investigational drug must be kept in an appropriate, limited-access, secure place until it is used or returned to the sponsor or designee for destruction. Investigational drug must be stored under the conditions specified on the label, and remain in the original bottle until dispensed. A daily temperature log of the drug storage area must be maintained every working day.

Temperature excursion must be reported to the sponsor or designee.

8.1.3 Dose and Regimen

Subjects will be dispensed 1 bottle of study medication at Visit 2 (Day -1) and will be required to take 2 capsules daily, 1 in the morning and 1 in the evening with food and approximately 240 mL of water. Subjects will be instructed to start study medication in the morning of the following day (Day 1).

[Table 8.a](#) describes the dose and regimen as it will be administered to each subject in each treatment group during the 4 weeks of the Double-Blind Treatment Period.

Table 8.a Dose and Regimen

Treatment Group	Dosage	Timing of Dose and Regimen	
		Morning (AM)	Evening (PM)
Placebo	1 placebo capsule taken by mouth BID for 4 weeks	Administered orally at breakfast with food and 240 mL of water	Administered orally at dinner with food and 240 mL of water
Lubiprostone	1 lubiprostone 24 µg capsule taken by mouth BID for 4 weeks		

8.1.4 Overdose

An overdose is defined as a known deliberate or accidental administration of investigational drug, to or by a study subject, at a dose above that which is assigned to that individual subject according to the study protocol.

All cases of overdose (with or without associated AEs) will be documented on an Overdose page of the eCRF, in order to capture this important safety information consistently in the database. Cases of overdose without manifested signs or symptoms are not considered AEs. AEs associated with an overdose will be documented on AE eCRF according to Section [10.0](#), Pretreatment Events and Adverse Events.

Serious adverse events (SAEs) associated with overdose should be reported according to the procedure outlined in Section [10.2.2](#), Collection and Reporting of SAEs.

In the event of drug overdose, the subject should be treated symptomatically.

8.2 Investigational drug Assignment and Dispensing Procedures

The investigator or investigator's designee will access the IVRS/IWRS at Screening/ Visit 1 to obtain the subject study number.

After study eligibility is confirmed (ie, At Visit 2), the investigator or the investigator's designee will utilize the IVRS/IWRS to randomize the subject into the study. During this contact, the investigator or designee will provide the necessary subject-identifying information, including the subject number assigned at screening. The MED ID number of the investigational drug to be dispensed will then be provided by the IVRS/IWRS.

If the investigational drug is lost or damaged, the site can request a replacement from IVRS/IWRS. (Refer to IVRS/IWRS manual provided separately.)

If a dose was missed, the subject is to leave the capsule in the bottle and resume regular administration at the next scheduled dose time. The subject is instructed to note the missing dose in the daily diary.

Instructions for subjects on how to store investigational drug will be provided by the investigator or investigator's designee.

Unused medication should be returned at Visit 5.

8.3 Randomization Code Creation and Storage

The sponsor or designee will generate the randomization schedule prior to the start of the study; IVRS/IWRS will be used in a centralized fashion for subject randomization and study medication assignments. All randomization information will be stored in a secured area, accessible only by authorized personnel.

8.4 Investigational Drug Blind Maintenance

The investigational drug blind will be maintained using the IVRS/IWRS.

8.5 Unblinding Procedure

The investigational drug blind shall not be broken by the investigator unless information concerning the investigational drug is necessary for the medical treatment of the subject. In the event of a medical emergency, if possible, the medical monitor should be contacted before the investigational drug blind is broken to discuss the need for unblinding.

For unblinding a subject, the investigational drug blind can be obtained by the investigator, by accessing the IVRS/IWRS.

The sponsor must be notified as soon as possible if the investigational drug blind is broken. The date, time, and reason the blind is broken must be recorded in the source documents and the same information (except the time) must be recorded on the eCRF.

If any site personnel are unblinded, investigational drug must be stopped immediately and the subject must be withdrawn from the study.

CONFIDENTIAL

8.6 Accountability and Destruction of sponsor-Supplied Drugs

Drug supplies will be counted and reconciled at the site before being returned to the sponsor or designee.

The investigator or designee must ensure that the sponsor-supplied drug is used in accordance with the protocol and is dispensed only to subjects randomized in the study. To document appropriate use of sponsor-supplied drug (lubiprostone and matching placebo), the investigator or designee must maintain records of all sponsor-supplied drug delivery to the site, site inventory, dispensation and use by each subject, and return to the sponsor or designee.

Upon receipt of sponsor-supplied drug, the investigator or designee must verify the contents of the shipments against the packing list. The verifier should ensure that the quantity is correct, and the medication is in good condition. If quantity and conditions are acceptable, investigator or designee should acknowledge the receipt of the shipment by recording in IVRS/IWRS. If there are any discrepancies between the packing list versus the actual product received, Takeda must be contacted to resolve the issue. The packing list should be filed in the investigator's essential document file.

The investigator or designee must maintain 100% accountability for all sponsor-supplied drugs received and dispensed during his or her entire participation in the study. Proper drug accountability includes, but is not limited to:

- Continuously monitoring expiration dates (if the expiry date is provided to the investigator).
- Frequently verifying that actual inventory matches documented inventory.
- Verifying that the log is completed for the MED ID.
- Verifying that all containers/ bottles used are documented accurately on the log.
- Verifying that required fields are completed accurately and legibly.

If any dispensing errors or discrepancies are discovered, the sponsor must be notified immediately.

The IVRS/IWRS will include all required information as a separate entry for each subject to whom sponsor-supplied drug is dispensed.

The investigator or designee must record the current inventory of all sponsor-supplied drugs lubiprostone and matching placebo on a sponsor-approved drug accountability log. The following information will be recorded at a minimum: protocol number and title, name of investigator, site identifier and number, description of sponsor-supplied drugs, expiry date, date and amount dispensed including initials or signature of the person dispensing the drug, and the date and amount returned to the site by the subject, including the initials or signature of the person receiving the sponsor-supplied drug. The log should include all required information as a separate entry for each subject to whom sponsor-supplied drug is dispensed.

All study drug that was not returned to the site by a subject must be investigated by the site and appropriately documented on the drug accountability log.

Prior to site closure or at appropriate intervals, a representative from the sponsor or its designee will perform sponsor-supplied drug accountability and reconciliation before sponsor-supplied drugs are returned to the sponsor or its designee for destruction. The investigator or designee will retain a copy of the documentation regarding sponsor-supplied drug accountability, return, and/or destruction, and originals will be sent to the sponsor or designee.

The investigator will be notified of any expiry date or retest date extension of sponsor-supplied drug during the study conduct. On expiry date notification from the sponsor or designee, the site must complete all instructions outlined in the notification, including segregation of expired sponsor-supplied drug for return to the sponsor or its designee for destruction.

In the event of expiry date extension of sponsor-supplied drug already at the study site, sponsor-supplied drugs may be relabeled with the new expiry date at that site. In such cases, Takeda or its designee will prepare additional labels, certificates of analyses, and all necessary documentation for completion of the procedure at the sites.

9.0 STUDY PLAN

9.1 Study Procedures

The following sections describe the study procedures and data to be collected. For each procedure, subjects are to be assessed by the same investigator or site personnel whenever possible. The Schedule of Study Procedures is located in [Appendix A](#).

9.1.1 Informed Consent Procedure

The requirements of the informed consent are described in Section [15.2](#) and [Appendix C](#).

Informed consent must be obtained prior to the subject entering into the study, and before any protocol-directed procedures are performed.

A unique subject identification number (subject number) will be assigned to each subject at the time that informed consent is obtained; this subject number will be used throughout the study.

9.1.2 Demographics, Medical History, and Medication History Procedure

Demographic information to be obtained will include age, sex, race as described by the subject, and smoking status of the subject at Screening.

Medical history to be obtained will include determining whether the subject has any significant conditions or diseases relevant to the disease under study that stopped at or prior to signing of informed consent. Ongoing conditions are considered concurrent medical conditions (see Section [9.1.11](#)).

Medication history information to be obtained includes any medication relevant to eligibility criteria and efficacy/safety evaluation stopped at or within 1 month prior to signing of informed consent.

9.1.3 Physical Examination Procedure

A Baseline physical examination (defined as the assessment prior to first dose of investigational drug) will consist of the following body systems: (1) eyes; (2) ears, nose, throat; (3) cardiovascular system; (4) respiratory system; (5) gastrointestinal system; (6) dermatologic system; (7) extremities; (8) musculoskeletal system; (9) nervous system; (10) lymph nodes; (11) genitourinary system; and (12) other. All subsequent physical examinations should assess clinically significant changes from the assessment prior to first dose examination.

9.1.4 Weight, Height

A subject should have weight and height measured while wearing indoor clothing and with shoes off. Height will be measured at Visit 1 and weight will be measured at Visit 1 and 5. The standard for collecting height is centimeters without decimal places and for weight it is kilograms (kg) with 1 decimal place.

9.1.5 Vital Sign Procedure

Vital signs will include body temperature, respiratory rate, sitting blood pressure (resting more than 5 minutes), and pulse (bpm).

9.1.6 Primary Efficacy Endpoint

The primary efficacy endpoint is SBM frequency at Week 1, the data for which will be collected in a subject diary; see [Appendix E](#). Subjects will be given a diary to complete at home, where they will record the date and time of each BM.

9.1.7 Secondary Efficacy Endpoints

9.1.7.1 SBM Frequency at Weeks 2, 3 and 4

This secondary endpoint will be collected as specified for the primary analysis.

9.1.7.2 Proportion of Subjects Who Have a SBM Within 24 Hours After First Dose

The proportion of subjects with an SBM within 24 hours after first dose in Week 1 will be assessed and derived from the data on SBMs collected in the subject diary.

9.1.7.3 Degree of Straining

For each subject, the degree of straining will be scored on a 5-point scale, with a higher score indicating more severe straining, and averaged for all SBMs at Weeks 1, 2, 3, and 4. The degree of straining for each SBM will be collected in the subject diary.

9.1.7.4 Stool Consistency

Stool consistency will be scored using the Bristol Stool Chart (see [Appendix E](#)) and the mean provided for all SBMs at Weeks 1, 2, 3 and 4. Stool consistency will be collected in the subject diary for each SBM recorded.

9.1.7.5 Assessments of Abdominal Symptoms

The abdominal symptoms (bloating and discomfort upon waking in the morning) will be scored weekly on a 5-point scale, with a higher score indicating more severe symptoms. This will be assessed at Baseline and at Weeks 1, 2, 3, and 4. Subjects will be instructed to record weekly abdominal symptoms assessment in the diary. Diary entries will be reviewed at each Study Visit as per protocol schedule.

9.1.8 Additional Endpoints

9.1.8.1 Quality of Life Evaluation

The PAC-QOL is a health related QOL instrument designed specifically to evaluate an adult subject's assessment of constipation over time. It is self -administered assessment consisting of

28 items and is designed to cover the 2 weeks prior to the questionnaire being completed. Each item is scored from 0 to 4; a lower score is better. The 28 items are grouped into 4 subscales: physical discomfort, psychosocial discomfort, worries and concerns, and satisfaction.

The PAC-QOL will be assessed at Day -1 (prior to the start of study drug), mid-way through the Double-Blind Treatment Period on Day 15, and at the end of the Double-Blind Treatment Period, on Day 29.

9.1.8.2 Safety Endpoints

Safety endpoints include adverse events, vital signs, clinical laboratory tests, physical examinations, and body weight.

9.1.9 Exploratory Endpoint

CCI

9.1.10 Documentation of Concomitant Medications

Concomitant medication is any drug given in addition to the study medication. These may be prescribed by a physician or obtained by the subject over the counter. Concomitant medication is not provided by Takeda. At each study visit, subjects will be asked whether they have taken any medication other than the study medication (used from signing of informed consent through the end of the study), and all medication including vitamin supplements, over-the-counter medications, and oral herbal preparations, must be recorded in the eCRF.

9.1.11 Documentation of Concurrent Medical Conditions

Concurrent medical conditions are those significant ongoing conditions or diseases that are present at signing of informed consent. This includes clinically significant laboratory, electrocardiogram (ECG), or physical examination abnormalities noted at the screening examination. The condition (ie, diagnosis) should be described.

9.1.12 Procedures for Clinical Laboratory Samples

All samples will be collected in accordance with acceptable laboratory procedures. The maximum volume of blood at any single visit is approximately 8 mL, and the approximate total volume of blood for the study is 24 mL.

Details of these procedures will be provided in the Central Laboratory Manual.

[Table 9.a](#) presents the clinical laboratory tests that will be utilized during this study.

Table 9.a Clinical Laboratory Tests

Hematology	Serum Chemistry	Urinalysis
RBC	ALP	Qualitative urinalysis (a)
WBC with differential	Albumin	
Hemoglobin	ALT	
Hematocrit	AST	
Platelets	Total bilirubin	
MCV	Direct bilirubin	
MCH	Total protein	
RDW	Total Cholesterol	
	Triglyceride	
	Glucose	
	Creatinine	
	BUN	
	Creatine kinase	
	Uric acid	
	GGT	
	LDH	
	Potassium	
	Sodium	
	Chloride	
	Calcium	
	Phosphorous	
	Magnesium	
	TSH (Visit 1)	
	CRP (Visit 1)	

Other:

Serum:	Urine:
Female subjects only: Beta hCG (for pregnancy) Visits 1 and 5 female subjects of childbearing potential only	Female subjects only: hCG for pregnancy Visit 2 female subjects of childbearing potential only. Drug screen for drugs of abuse at Visit 1

BUN=blood urea nitrogen, CRP= C-reactive protein, GGT= gamma-Glutamyl Transpeptidase, hCG=human chorionic gonadotropin, hpf=high-power field, LDH= lactic dehydrogenase, MCH=mean corpuscular hemoglobin, MCV=mean corpuscular volume, RBC= red blood cell, RDW=red (cell) distribution width, TSH= thyroid-stimulating hormone, WBC=white blood cell.

(a) Qualitative urinalysis: pH, specific gravity, protein, glucose, occult blood, urobilinogen, bilirubin, ketone and, leukocyte esterase.

(b) Microscopic analysis: RBC/hpf, WBC/hpf, epithelial cells, casts, etc.

Blood is collected for hematology and blood biochemistry, and urine is collected for urinalysis at Visit 1 (screening), and Visit 5 (at the completion of the Double-Blind Treatment Period), and, if applicable, at an Early Termination Visit. Women of childbearing potential undergo pregnancy test by serum at Visit 1 and 5 (or Early Termination Visit) and by urine at Visit 2. No pregnancy test is performed on women who have not menstruated for a year or longer.

The central laboratory will perform laboratory tests for hematology, serum chemistries, and urinalysis (excluding pregnancy tests). The results of laboratory tests will be returned to the investigator, who is responsible for reviewing and filing these results.

If subjects experience ALT or AST $>3 \times \text{ULN}$, follow-up laboratory tests (at a minimum, serum alkaline phosphatase, ALT, AST, total bilirubin, GGT, and INR) should be performed within a maximum of 7 days and preferably within 48-72 hours after the abnormality was noted.

(Please refer to Section 7.5 for discontinuation criteria, and Section 10.2.3 for the appropriate guidance on Reporting of Abnormal Liver Function Tests in relation to ALT or AST $>3 \times \text{ULN}$ in conjunction with total bilirubin $>2 \times \text{ULN}$.)

If the ALT or AST remains elevated $>3 \times \text{ULN}$ on these 2 consecutive occasions the investigator must contact the Medical Monitor for consideration of additional testing, close monitoring, possible discontinuation of study medication, discussion of the relevant subject details and possible alternative etiologies. The abnormality should be recorded as an AE (please refer to Section 10.2.3 Reporting of Abnormal Liver Function Tests for reporting requirements).

The investigator will maintain a copy of the laboratory accreditation and the reference ranges for the laboratory used.

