7.1 Inclusion Criteria

Subject eligibility is determined according to the following criteria prior to entry into the study:

1. In the opinion of the investigator, the subject is capable of understanding and complying with protocol requirements.
2. The subject or, when applicable, the subject's legally acceptable representative signs and dates a written, informed consent form and any required privacy authorization prior to the initiation of any study procedures.
3. The subject has a history of constipation defined as having SBM frequency of less than 3 times per week on average for 6 months or longer and for whom the same SBM frequency is observed during the Screening Period.
4. The subject has had 1 or more of the symptoms associated with SBM (described below) for 6 months or longer at the start of screening:
 - a) Scybalum stool or hard feces in at least 1 out of every 4 bowel movements.
 - b) Sensation of incomplete evacuation in at least 1 out of every 4 bowel movements.
 - c) Straining in at least 1 out of every 4 bowel movements.
5. The subject rarely has loose stools without the use of laxatives.
6. The subject is willing and able to keep a diary on his/her own and willing and able to complete a questionnaire.
7. The subject is male or female and aged 18 years or older, at the time of signing an informed consent.
8. A female subject of childbearing potential* who is sexually active agrees to use routinely adequate contraception* from signing of informed consent throughout the duration of the study and 14 days after the last dose of study drug.

*Definitions and acceptable methods of contraception are defined in Section 9.1.13 Contraception and Pregnancy Avoidance Procedure and reporting responsibilities are defined in Section 9.1.14 Pregnancy.

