9.1.13 Contraception and Pregnancy Avoidance Procedure

From signing of informed consent, throughout the duration of the study, and for 14 days after last dose of study medication, female subjects of childbearing potential* who are sexually active with a non-sterilized male partner** must use adequate contraception. In addition they must be advised not to donate ova during this period.

*Females NOT of childbearing potential are defined as those who have been surgically sterilized (hysterectomy, bilateral oophorectomy or tubal ligation) or who are postmenopausal (eg, defined as at least 1 year since last regular menses with an FSH $>40 \text{ IU/L}$ or at least 5 years since last regular menses, confirmed before any study medication is implemented).

**Sterilized males should be at least 1 year postvasectomy and have confirmed that they have obtained documentation of the absence of sperm in the ejaculate.

An acceptable method of contraception is defined as one that has no higher than a 1% failure rate. In this study, where medications and devices containing hormones are included, the only acceptable methods of contraception are:

Table 9.b Acceptable Methods of Contraception

Barrier Methods (a)	Intrauterine Devices (IUDs)	Hormonal Contraceptives

• Male condom PLUS spermicide.• Cap (plus spermicidal cream or jelly) PLUS male condom and spermicide.• Diaphragm (plus spermicidal cream or jelly) PLUS male condom and spermicide.	
• Copper T PLUS condom or spermicide.• Progesterone T PLUS condom or spermicide.	
• Implants.• Hormone shot/injection.• Combined pill.• Minipill.• Patch.• Vaginal ring PLUS male condom and spermicide.

IUD= intrauterine device.

(a) Barrier methods: to be used each time the subject has intercourse.

Subjects will be provided with information on acceptable methods of contraception as part of the subject informed consent process and will be asked to sign a consent form stating that they understand the requirements for avoidance of pregnancy and donation of ova during the course of the study.

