During the course of the study, regular serum and urine hCG pregnancy tests will be performed for women of childbearing potential only, and subjects will receive continued guidance with respect to the avoidance of pregnancy as part of the study procedures ([Appendix A](#)). In addition to a negative serum hCG pregnancy test at Screening, subjects also must have a negative urine hCG pregnancy test prior to dispensing of study medication at Visit 2.

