- (d) Includes the results of screening for IBS. The results of enema X-ray examination or total colonoscopy performed in the past 2 years are referred to in order to determine organic disorders that can be ruled out. For subjects who have no history or show no current evidence of weight loss, anemia, or rectal bleeding, the examination results of the past 3 years may be used to rule out organic disorders.
- (e) Subject eligibility is to be reconfirmed for all criteria on Day -1, Randomization Day, including diary data.
- (f) Vital signs=blood pressure (systolic and diastolic), body temperature, and pulse rate.
- (g) Height will be measured at Visit 1 and weight will be measured at Visit 1 and 5.
- (h) Hematology: hemoglobin, hematocrit, RBC, WBC with differential, platelets, MCV, MCH, RDW.
- Serum chemistry: ALP, Albumin, ALT, AST, Total bilirubin, Direct bilirubin, Total protein, Total Cholesterol, Triglyceride, Glucose, Creatinine, BUN, Creatine kinase, Uric acid, GGT, LDH, Na, K, Cl, Ca, P, Mg, (TSH [performed to exclude hypothyroidism] and CRP levels are measured at Visit 1 only).
- Urinalysis: pH, specific gravity, protein, glucose, occult blood, urobilinogen, bilirubin, ketone and leukocyte esterase.
- Microscopic analysis (only if positive dipstick results).
- (i) In women of childbearing potential only. Serum hCG pregnancy test conducted at Screening and at Final Visit (Early Termination Visit), and urine hCG pregnancy test conducted at Visit 2.
- (j) Diary-keeping by subjects will be continuous from Day -15 throughout the Screening Period and the Double-Blind Treatment Period to Day 29 (Final Visit). There will be no diary-keeping in the Follow-up Period.
- (k) Subjects who are not consistent or thorough with Study Diary completion may receive phone reminders if deemed necessary by the investigators. The authorized study personnel providing phone reminders must document the phone contact process in the subject's source notes.
- (l) Pretreatment adverse events: an adverse event in subjects who have signed informed consent to participate in the study that occurs prior to administration of any study medication; the event does not necessarily have to have a causal relationship with study participation. The pretreatment adverse events are assessed from Day -15 to hour 0 on Day 1, when study drug is administered.
- (m) Pregnancy reporting in Follow-Up Period occurs at 2 weeks after the last dose of study drug.

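### The one-year pregnancy-test exemption in Protocol 9.1.12 conflicts with 9.1.13, which pairs one year with FSH >40 IU/L or else asks for five years

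*Protocol*

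**What the plan says.** Protocol 9.1.12 gives two rules in consecutive sentences. The first sets the testing population and schedule: "Women of childbearing potential undergo pregnancy test by serum at Visit 1 and 5 (or Early Termination Visit) and by urine at Visit 2". The second exempts a group: "No pregnancy test is performed on women who have not menstruated for a year or longer".

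Inclusion criterion 8 (Protocol 7.1) sends the reader elsewhere for the terms: "Definitions and acceptable methods of contraception are defined in Section 9.1.13 Contraception and Pregnancy Avoidance Procedure". Section 9.1.13 then says "Females NOT of childbearing potential are defined as those who have been surgically sterilized", for which it names three operations, and adds postmenopausal women as a further group. It illustrates that group by two routes. The first is introduced with the words "who are postmenopausal (eg, defined as at least 1 year since last regular menses with an FSH", and the threshold it sets for FSH is above 40 IU/L. The second route needs no FSH result and reads "or at least 5 years since last regular menses, confirmed before any study medication is implemented".

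For women of childbearing potential, 9.1.13 adds a condition on dispensing beyond the negative serum test at Screening: "subjects also must have a negative urine hCG pregnancy test prior to dispensing of study medication at Visit 2".

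Table 9.a, the visit checklists in 9.3.1, 9.3.2 and 9.3.4, Appendix A note (i) and SAP Table 7.a all limit hCG testing to women of childbearing potential. None of them repeats the one-year exemption.

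**The concern.** The 9.1.12 exemption depends only on time since any menstruation. It asks for no FSH result and does not say that the absence of menses must be due to menopause. In 9.1.13, one year appears only together with a raised FSH, and the alternative without FSH is five years. A site cannot follow both sections for a woman who meets the 9.1.12 exemption but neither route in 9.1.13.

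What is at stake is subject safety and procedural clarity. Pregnancy is an exclusion (7.2, item 9) and a reason for immediate withdrawal (7.5, item 6). A site that relied on the exemption could dispense study drug to an untested woman who meets neither of the routes that 9.1.13 gives for postmenopausal status. A site that tested her would depart from the exemption as written.

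**Working it through.** This is a comparison of text. The plan gives no figure to reproduce and no power or sample-size formula applies.

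**1. Compare the two rules by group.** All rows are non-sterilised women.

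| Group | 9.1.12 exemption | 9.1.13 as illustrated | Conflict? |
|---|---|---|---|
| Menstruated within the past year, neither 9.1.13 route met | Does not apply: tested | Childbearing potential: tested | No |
| No menses ≥1 year, <5 years since last regular menses, FSH >40 IU/L documented | Exempt | Postmenopausal: not tested | No |
| No menses ≥1 year, <5 years since last regular menses, FSH ≤40 IU/L or not documented | Exempt | Neither route met: tested, with a negative urine hCG before dispensing | **Yes** |
| No menses ≥1 year, ≥5 years since last regular menses | Exempt | Postmenopausal: not tested | No |

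Only the third row conflicts. Women with irregular bleeding in the past year are outside it, because the 9.1.12 exemption does not reach them.

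**2. Does *eg* in 9.1.13 remove the conflict?** Suppose one year alone were enough. The FSH condition would then add nothing. The five-year route would also add nothing, since any woman at five years has already passed one year. The examples make sense only if one year alone is not meant to suffice. The word does leave the description open to other grounds for judging a woman postmenopausal, so the boundary is not fully fixed.

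**3. Width of the window.** 5 − 1 = 4, so up to 4 years since last regular menses.

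**4. Tests omitted per affected woman (9.1.12).** Serum at Visit 1 + urine at Visit 2 + serum at Visit 5 or Early Termination = 3. Before the first dose on Day 1: Visit 1 + Visit 2 = 2.

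**5. Would the study itself supply an FSH result?** Table 9.a lists 8 haematology tests and 24 serum chemistry tests (including TSH and CRP at Visit 1): 8 + 24 = 32, of which FSH is 0. Appendix A note (h) and SAP Table 7.a also omit it. A documented FSH would therefore have to come from outside the scheduled panel. The documents do not say how often one would be available.

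**The case against.** The strongest counter-argument is that the protocol already contains the protective rule in several places. The sentence just before the exemption requires testing in women of childbearing potential, 9.1.13 makes a negative urine test a condition of dispensing, and Table 9.a, the checklists and Appendix A note (i) agree. Only one sentence departs from this, and it matters only if a site lets it override the others. Guidance on avoiding pregnancy is also given at every visit. This stands, and it limits the practical risk. It does not remove the conflict, because the other places rely on childbearing potential without defining it, while the exemption is categorical.

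A second argument is that *eg* makes the routes in 9.1.13 examples only. This stands in part. A reader might infer that 9.1.13 firmly classes every woman in the window as of childbearing potential; the text does not go that far. It shows that one year alone was not meant to be enough, and no more.

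A reader might also infer that Appendix A and the visit checklists contradict 9.1.12 directly. They do so only through the definition in 9.1.13.

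Finally, the absence of FSH from the panel does not show that FSH will be missing. Section 9.1.13 requires status to be confirmed before study medication and does not say that the result must come from the study laboratory.

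**Conclusion.** The exemption sentence in 9.1.12 is wrong as written. It conflicts with 9.1.13 for non-sterilised women with no menses for at least 1 year, less than 5 years since last regular menses, and no documented FSH >40 IU/L. For each such woman, a literal reading drops 3 hCG tests, 2 of them before the first dose.

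Confidence is moderate. The conclusion rests on reading the examples in 9.1.13 so that the FSH condition and the five-year route both have a purpose. The documents give no split by sex or menopausal status, so the number of women affected cannot be stated. The primary analysis, sample size and type I error are untouched. The correction is worth making but is not essential to the trial's validity.

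**What to change.** Replace the exemption sentence in 9.1.12 with: *No pregnancy test is performed on women not of childbearing potential as defined in Section 9.1.13; a non-sterilised woman with 1 to <5 years since last regular menses and no documented FSH >40 IU/L is tested.* The second clause makes the testing rule explicit, so it does not depend on how *eg* is read.

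Leave *eg* in 9.1.13. Deleting it looks like a natural companion edit but has a drawback. The five-year route counts from last regular menses and needs no FSH. As a fixed definition, it would automatically class a woman who still bleeds irregularly, with her last regular menses at least five years ago, as not of childbearing potential. The new cross-reference would then exempt her from testing. The present wording leaves room to judge that she is not postmenopausal.

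The cost is one sentence and at most 3 extra hCG tests per affected woman, of kinds already scheduled. No FSH assay is needed, because a woman in the window without a documented result above 40 IU/L is simply tested. The contraception rules in 9.1.13 are not changed.
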